#### 11.1.2. Veledimex

The veledimex product is supplied as a 50 mg/g Solutol™ formulation, encapsulated in Licaps® hard gelatin capsules to produce veledimex at a strength of 40 mg per capsule.

#### Packaging and Labeling

##### Veledimex Hard Gelatin Capsules, 40 mg (Solutol®)

Study No.: XXXXX

Lot No.: XXJM-XXX

Manufacturing Date: DDMMYYYY

Contains 30 capsules / bottle

Storage Conditions: 15°C - 25°C

For Oral Administration Only

**Caution: New Drug – Limited by Federal (or United States) Law for Investigational Use Only**

Manufactured for Fibrocell Technologies, Inc. by Capsugel® (Now a Lonza Company)

[name]

The manufacturing location may be revised during the course of the study.

### **Storage**

The primary container closure system for veledimex drug product packaged clinical supplies is 75 cc white HDPE, round bottle with 33 mm white child resistant closure.

Veledimex capsules should be stored at room temperature under dry conditions. Intact veledimex capsules can be considered to be nontoxic and can be safely handled without special precautions.

### **Preparation and Administration**

For the current study, veledimex is intended to be administered once daily at a maximum daily dose of 160 mg (4 capsules containing 40 mg veledimex each).

### **11.2. Study Drug Accountability**

An accurate record of all supplies received and used at each site should be maintained and updated regularly.

Subject will be instructed to return all veledimex capsules at specified protocol visits for study treatment inventory and assessment of subject compliance.

The dispensing and return of all veledimex will be recorded on the study Investigational Product Dispensing Record. The Subject Number and the initials and date of the person dispensing and receiving the returned treatment will be documented on this form.

Inventory records must be readily available for inspection by the study monitor and/or auditor, and open to inspection by regulatory authorities at any time.

### **11.3. Study Drug Handling and Disposal**

After receipt of the shipped vials, they must be kept sealed in the shipper until ready for use. The Investigator will be responsible for accurate, written records of all FCX-013 received. The Sponsor or designee will be permitted upon request to audit the administration procedures and records.

FCX-013 Drug Product will be shipped same day or overnight delivery to the clinic and must be administered within 40 hours of the fill time as indicated on the label.

## **12. ADVERSE EVENTS**

Adverse events will be collected from the time the subject signs the informed consent form (ICF) until the final visit/contact with the subject.

At each visit/contact, the Investigator or designee is responsible for reviewing, documenting, and reporting events that meet the definition of an AE.

Subjects should be asked a non-leading question in order to avoid bias in eliciting AEs, such as “Have you had any changes in your health since your last visit?” at each visit/contact. It is important to question the subject in a non-leading way about changes in their health or concomitant medication usage since their last visit.

\* For any subject who develops an AE suggestive of a retrovirus-associated disease after FCX-013 treatment, attempts will be made to collect any relevant clinical samples for available RCL testing

\*For any subject who dies or is diagnosed with a neoplasm after FCX-013 treatment, attempts will be made to collect a biopsy of the neoplastic tissue or pertinent autopsy tissue to assay for available RCL testing by qPCR.

Following the subject’s initial report of an AE, the Investigator or designee is required to proactively follow-up with the subject regarding any previous AE that hasn’t resolved at subsequent visits/contacts.

### **12.1. Adverse Event Definitions**

An AE is any untoward medical occurrence associated with the use of a drug in humans, whether or not considered drug related. An AE can therefore be any unfavorable and unintended sign (including an abnormal laboratory finding), symptom, disease or exacerbation of a pre-existing condition temporally associated with the use of a medicinal (investigational) product.

Signs and/or symptoms of the disease under study/lack of efficacy should not be considered as AEs, as long as they are within the normal day-to-day fluctuation or expected progression of the disease. However, significant worsening (e.g., increase in severity or frequency) of the signs and/or symptoms should be recorded as an AE. Any clinically significant change from Screening, based upon the opinion of the Investigator, in physical or examination findings and/or vital signs should be recorded as an AE.

A change in the value of a safety laboratory evaluation can represent an AE if the change is clinically significant, based upon the opinion of the Investigator, or if, during treatment with the IP, a shift of a parameter is observed from a normal value to a pathological value, or a further worsening of an already pathological value. When evaluating such changes, the extent of deviation from the reference range, the duration until return to the reference range, either while continuing treatment or after the end of treatment with the IP, and the range of variation of the respective parameter within its reference range, should be taken into consideration. The Investigator should decide, based on the above criteria and the clinical condition of the subject, whether a change in a laboratory parameter represents an AE. For pathological laboratory values that were not present prior to IP administration, follow-up laboratory evaluations should be performed until the values return to within reference range or until a plausible explanation is found.

Any AE occurring after administration of IP will be considered a TEAE.

Examples of events meeting the definition of an AE **include**:

- Any abnormal laboratory test results (hematology, chemistry) or other safety assessments (e.g., physical examination, vital signs measurements), including those that worsen from Screening, and felt to be clinically significant based upon the medical and scientific judgment of the Investigator;
- Exacerbation of a chronic or intermittent pre-existing condition (e.g., asthma) including either an increase in frequency and/or intensity/severity of the condition;
- New conditions detected or diagnosed after Screening.

Examples of events that **do not** meet the definition of an AE include:

- Any clinically significant abnormal laboratory findings or other abnormal safety assessments that are associated with the underlying disease, unless judged by the Investigator to be more severe than expected for the subject's condition (e.g., anemia);
- The disease/disorder being studied or expected progression, signs, or symptoms of the disease/disorder being studied, unless more severe than expected for the subject's condition or if these events meet the criteria as SAEs or leads to discontinuation of FCX-013 or from the study;
- Medical or surgical procedure (e.g., endoscopy, appendectomy); the condition that leads to the procedure is an AE;
- Anticipated day-to-day fluctuations of pre-existing disease(s) or condition(s) present or detected at the start of the study that do not worsen.

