## 2. SYNOPSIS

Name of Sponsor/Company: Fibrocell Technologies, Inc. (Fibrocell)		
Name of Investigational Product: FCX-013 + veledimex (FCX-013 plus veledimex)		
Name of Active Ingredient: FCX-013 (Genetically Modified Autologous Human Dermal Fibroblasts) Veledimex capsules for oral administration		
Protocol Number: FI-SC-001	Phase: 1/2	Country: USA
Title of Study: A Phase 1/2 Study of a Combination of FCX-013 (Genetically-Modified Autologous Human Dermal Fibroblasts) Plus Veledimex for the Treatment of Moderate to Severe Localized Scleroderma (Morphea)		
Study center(s): Up to 3 centers		
Studied period (years): Estimated date first subject screened: 4Q2019 Estimated date last subject completed: 2035 (includes long-term follow-up)		Phase of development: I Phase 1/2
Objectives: Primary: The primary objective of this protocol is to evaluate the safety of FCX-013 plus veledimex in subjects with moderate to severe localized scleroderma/morphea. Secondary: The secondary objective of this protocol is to evaluate the antifibrotic effects of FCX-013 plus veledimex via the LoSCAT (Localized Scleroderma Assessment Tool) and durometry.		
Methodology: This is an open-label, single arm Phase 1/2 study being conducted by Fibrocell to evaluate FCX-013 in subjects with moderate to severe localized scleroderma. Approximately ten subjects will be enrolled and receive FCX-013. The study is divided into the following periods: Screening (including Manufacturing of FCX-013), Treatment, and Long-Term Follow-Up. The Screening Period consists of evaluation of eligibility, the collection of one set of three 3-4 mm biopsies for the manufacture of FCX-013 product, and the identification of potential target sclerotic lesions. Due to the FCX-013 manufacturing process, the Screening Period is expected to have a duration of approximately 4-6 months; however, this period can be extended to accommodate subject scheduling, variations in manufacturing duration and protocol mandated delays (i.e. pauses due to staggered treatment).		

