**Safety:**

Safety evaluations will be based on listed AEs, physical examinations, vital signs, clinical laboratory evaluations, ECGs and prior/concomitant medications, and assessment for the presence of RCL antibodies. The AE severity will be described using National Cancer Institute (NCI) Common Terminology Criteria for Adverse Events (CTCAE) grades, using the current version at study start. AEs will be coded using the Medical Dictionary for Regulatory Activities (MedDRA; version 23.0 or later) and described by body system and preferred term, relationship to FCX-013, seriousness, and severity. AEs causing investigational product discontinuation and/or early study discontinuation, and serious adverse events (SAEs) will be noted.

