### **8.3. Subject Withdrawal Criteria**

A subject is free to withdraw from the study at any time for any reason without prejudice to their future medical care by the physician or at the institution. The Investigator or Sponsor may also withdraw the subject at any time in the interest of subject safety or for other reasons. Criteria for withdrawal include:

- Consent is withdrawn
- The subject refuses treatment and/or procedures/observations
- Occurrence of unmanageable AEs, or pregnancy
- For other reasons (e.g., significant protocol violation, non-compliance)

The Sponsor may be contacted if clarification is required.

The primary reason for withdrawal must be recorded on the case report form (CRF). Comments or complaints regarding the withdrawal made by the subject must also be recorded on the CRF. Withdrawal information will be communicated to the DSMB at each meeting. Withdrawal should be discussed with the medical monitor prior to withdrawal when possible. Subjects who wish to discontinue treatment or study procedures after receipt of FCX-013 will be asked to continue in the Long-Term Follow-Up Period.

Subjects who withdraw prior to FCX-013 administration will be considered a screen failure and will be replaced. The Sponsor reserves the right to terminate the study.

Discontinuation of FCX-013 administration does not mean discontinuation from the study. The study assessments and procedures for the visit and subsequent visits should be completed as indicated in the Schedule of Events ([Table 4](#)) and reason for discontinuation of FCX-013 administration should be documented in the subject's source documents and CRF.

If a subject discontinues from the study, every effort must be made to perform the study assessments and procedures specified for an Early Termination Visit (Week 12). The primary

reason for subject's withdrawal from the study should be documented in the subject's source documents and CRF.

Subjects who discontinue from the study following IP administration will be asked to participate in the Long-Term Safety Follow-up period.

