### 9.2. Investigational Product Dosing

#### FCX-013

Subjects will receive intradermal injections of FCX-013 to treatment lesion(s) in a single treatment session, on Day 1.

[Table 2](#) provides details regarding the number of cells, vials and injections per treatment session.

A treatment session of FCX-013 will consist of a maximum of 4 mL of FCX-013 administered in up to sixteen (16) 0.25 mL intradermal injections. The injections will be administered around the perimeter of the sclerotic target lesion(s), approximately 1 cm apart. The Investigator will attempt to administer the full 4 mL of FCX-013. Additional details of FCX-013 administration can be found in [Appendix 2](#).

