#### Veledimex

Veledimex will be administered once daily, starting on Day 1 following FCX-013 injection. The veledimex dose is 160 mg daily (4 capsules containing 40 mg veledimex each), for 14 days.

Veledimex must be taken with food. Compliance with veledimex administration will be verified at the Week 2 visit, based on subject report and capsule count (accountability).

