### **10.2.3. Week 2 (Day 15) / Week 4 (Day 29)**

At Week 2, remaining veledimex should be collected, and the subject should be queried about their dosing compliance, including any dates of missed doses, and this information should be recorded.

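### Section 12.1 counts an expected disease event as an AE if it stops FCX-013, given once on Day 1, but not if it stops the 14-day veledimex course, leaving a narrow gap in the primary safety data

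*Protocol*

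**What the plan says.** Protocol Section 12.1 lists examples of events that are not AEs. One is the disease under study, with its expected progression, signs and symptoms. The example has exceptions: the event is an AE after all if it is more severe than expected for that subject, or "if these events meet the criteria as SAEs or leads to discontinuation of FCX-013 or from the study".

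On dosing, Section 9.2 states: "Subjects will receive intradermal injections of FCX-013 to treatment lesion(s) in a single treatment session, on Day 1". For the second component it states: "The veledimex dose is 160 mg daily (4 capsules containing 40 mg veledimex each), for 14 days". Veledimex starts on Day 1 after the injection. The Synopsis and Table 1 present both components as investigational product.

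On recording reasons, Section 8.3 says the "reason for discontinuation of FCX-013 administration should be documented in the" source documents and CRF. It asks separately for the primary reason for withdrawal from the study. At Week 2, Section 10.2.3 has the subject asked about veledimex compliance, "including any dates of missed doses, and this information should be recorded".

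On reporting, the Safety paragraph of the Synopsis commits to noting "AEs causing investigational product discontinuation and/or early study discontinuation".

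**The concern.** The 12.1 exception ensures that a disease event with a consequence for treatment is counted even when its severity alone would not make it an AE. It names the component that is finished on Day 1 and omits the one the subject goes on taking. The Synopsis category covers the whole product, so the definition and the planned report do not match.

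Safety is the primary objective, and the trial is single-arm and open-label, so the investigator alone judges whether a lesional sign is expected. Erythema and induration are LoSCAT items; skin pain, burning and itch are SkinDex items. If a reaction to treatment resembled one of these (an assumption, not a statement in the protocol), it could be read as expected disease. The discontinuation trigger depends less on that judgement, and it does not cover veledimex. An SAP cannot repair this, because an event never recorded as an AE is not in the AE data. A subject with fewer than 10 veledimex doses also leaves the per-protocol population under Section 13.2, and the reason for the shortfall need not be recorded.

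**Working it through.** The plan states no figure to reproduce. The check sets the provisions side by side.

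1. **What can be discontinued, and when.** FCX-013: one session on Day 1. Veledimex: 14 daily doses, all after the injection, of which 14 − 1 = 13 fall after Day 1. Once the session is over, any discontinuation of treatment is a discontinuation of veledimex.

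2. **Does stopping veledimex count as leaving the study?** No. Section 7.5.2 keeps subjects who voluntarily cease treatment in follow-up unless they withdraw consent. The study-discontinuation limb of 12.1 is therefore not triggered by stopping veledimex alone.

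3. **Test case.** Take a non-serious disease symptom within the expected course that makes a subject stop veledimex between Day 2 and Day 14 while staying in the study.

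| Route to becoming an AE | Met? |
|---|---|
| More severe than expected (12.1) | No, by construction |
| Meets SAE criteria (12.1) | No, by construction |
| Leads to discontinuation of FCX-013 (12.1) | No, the session is already complete |
| Leads to discontinuation from the study (12.1) | No, the subject stays |
| Significant worsening of disease signs or symptoms (12.1) | No, severity and frequency are not increased |
| Clinically significant change from Screening in examination findings or vital signs (12.1) | No, by construction |

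The event is not an AE, so it cannot appear among the AEs causing product discontinuation that the Synopsis says will be noted.

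4. **Is the reason captured elsewhere?** Section 8.3 requires it for FCX-013 and for study withdrawal. Section 10.2.3 requires the dates of missed veledimex doses. Section 7.5.2 lists reasons for which the investigator or sponsor may stop treatment, but does not ask that the applicable one be recorded. Section 12.2 requires the actions taken, but only for an event that is already an AE. None requires the reason for stopping veledimex.

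5. **Same case with veledimex named in the exception.** The event becomes an AE and enters the Synopsis category.

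**The case against.** The strongest reply is that little is left once the rest of the protocol is applied, and much of that stands.

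- Any event other than a sign of the disease that stops veledimex is already an AE under the general definition. A reader might infer that treatment-stopping events in general go uncounted; the protocol does not support that.
- Significant worsening and clinically significant change are AEs whatever happens to treatment. Inclusion criterion 2 requires clinically inactive disease for 3 months before Screening and through Day 1, so a disease symptom that newly leads to a stop within two weeks would often be caught as worsening.
- A reader might call the FCX-013 limb empty. It is not: AEs are collected from consent, and a disease event could lead to the session being withheld or to a series of up to 16 injections being cut short.
- Section 8.3 lists refusal of treatment as a withdrawal criterion. A subject withdrawn on that ground has a recorded reason and meets the study-discontinuation limb. Only a subject kept in the study under Section 7.5.2 escapes.
- The Week 2 compliance query is not limited to dates, so a site may well note why doses were missed. It is therefore too strong to say that such a subject could never be told from one who forgot capsules. What stands is that the protocol does not require the note.
- One subject in about ten is 1/10 = 10 percentage points. A reader might take that as the expected distortion; it is only the weight of a single case.

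These points limit the size of the gap. They do not explain why the exception names one component while the Synopsis commits to reporting on the product as a whole.

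**Conclusion.** The point holds in narrow form. Sections 12.1 and 8.3 name only FCX-013 where the Synopsis commitment covers both components. One kind of event is lost: related to the disease, non-serious, judged no worse than expected, not a clinically significant change, and followed by a stop of veledimex without study withdrawal. Its frequency cannot be estimated from the protocol and may be low. This is a small defect in a definition. It deserves correction because safety is the primary objective, about 10 subjects are planned, and the loss cannot be undone at analysis. The conclusion rests on reading the 12.1 exceptions literally and on Section 7.5.2 keeping subjects who stop treatment in the study.

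**What to change.** Reconcile the passages as follows.

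- **Section 12.1:** in the exception for disease events, change *discontinuation of FCX-013* to *discontinuation of FCX-013 or veledimex*.
- **Section 8.3:** make the same change in the sentence on documenting the reason for discontinuation.
- **Section 10.2.3:** at Week 2, record the reason for any permanent stop of veledimex.

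Do not extend the exception to interruptions. Neither the present clause nor the Synopsis commitment covers them, and a skipped dose with unchanged symptoms could then become an AE. No dose or stopping rule is affected.

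The cost is wording in three places and one CRF field. The downside is that an occasional extra disease-related AE may be counted, for example when a subject stops because unchanged symptoms are seen as lack of effect. The recorded reason would let a reader recognise such cases.

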### 12.1.1. Serious Adverse Event

An AE or suspected adverse reaction is considered "serious" if, in the view of either the investigator or sponsor, it results in any of the following outcomes:

- Death
- A life-threatening AE
  - An AE or suspected adverse reaction is considered "life-threatening" if, in the view of either the investigator or sponsor, its occurrence places the subject at immediate risk of death. It does not include an AE or suspected adverse reaction that, had it occurred in a more severe form, might have caused death)
- Inpatient hospitalization or prolongation of existing hospitalization
  - Emergency room visits that do not result in admission to the hospital should be evaluated for one of the other serious outcomes (e.g., life-threatening; required intervention to prevent permanent impairment or damage; other serious medically important event).

- A persistent or significant incapacity or substantial disruption of the ability to conduct normal life functions
- A congenital anomaly/birth defect
- Important medical events that may not result in death, be life-threatening, or require hospitalization may be considered serious when, based upon appropriate medical judgment, they may jeopardize the subject and may require medical or surgical intervention to prevent one of the outcomes listed in this definition. Examples of such medical events include allergic bronchospasm requiring intensive treatment in an emergency room or at home, blood dyscrasias or convulsions that do not result in inpatient hospitalization, or the development of drug dependency or drug abuse.
- Any event that does not exactly meet this definition yet, in the investigator's opinion represents a significant hazard can be assigned the "important medical events" regulatory reporting serious criteria.

## **12.2. Reporting Procedure**

All AEs observed by the Investigator or site staff or reported by the subject or their caregiver (whether or not attributed to IP), must be fully and completely documented in the subject's source documents and CRF. In the event a subject is withdrawn from the study because of an AE, the primary reason for withdrawal (i.e., due to an AE) must be recorded on the CRF as such.

Each AE requires a complete description including event description (where possible, a diagnosis or if a diagnosis has not been made, individually listed sign(s)/symptom(s)), date of onset and resolution, if applicable, outcome (refer to Section 12.2.2), and actions taken to be recorded in the source documents. The Investigator must also assign the following attributes for each AE: its relationship to the IP (refer to Section 12.2.3) and severity of the AE (refer to Section 12.2.4). The Investigator may be asked to provide follow-up information.

